10.3.12. Assessment of Site Homogeneity

Homogeneity of the primary safety and effectiveness endpoints across sites will be assessed with a chi-square test of proportions at an alpha level of 0.1 and will be conducted on the mITT population set for the safety endpoint and on the PP population set for the effectiveness endpoints using the observed data only for both. Sites with less than 5 subjects will be pooled.

10.4. Measures to Minimize Bias

Pulsar Vascular, Inc. will be diligent in controlling for bias by utilizing proper study design and implementation of the approved study protocol. IRB approval will be obtained at all clinical sites prior to study initiation. Study agreements/contracts will be made with the hospitals/universities and all compensation for conduct of the study will be paid to the hospitals/universities and not to the investigators. Strict inclusion and exclusion criteria will be implemented to avoid selection bias.

Investigators will assess potential subjects who are candidates for the study. In addition, an image of the subject's aneurysm and branch arteries must be reviewed and approved by the Image Screening Committee. Candidates who meet the protocol inclusion/exclusion criteria with at least one bifurcation intracranial aneurysm that is acceptable for minimally invasive treatment and approved by the Image Screening Committee may be enrolled.

A Clinical Events Committee (CEC) will review all reportable adverse events and adjudicate endpoints to determine whether they meet protocol-specified criteria. The CEC will review all reportable adverse events to adjudicate the safety endpoint, in addition to AEs of interest specified in the CEC charter. CEC members will provide an impartial review and will not hold a financial interest in Pulsar Vascular, Inc. An independent core laboratory will perform the angiographic assessments for the primary and secondary effectiveness endpoints. These evaluations will be performed by an independent reader who does not hold a financial interest in Pulsar Vascular, Inc.

Clinical outcomes will be measured in a standardized manner using the National Institutes of Health Stroke Scale, a standardized, objective, clinical assessment tool used to quantify and document the neurological status of patients and to act as a predictor for clinical outcomes. It is used to determine stroke and the severity of stroke.

Clinical outcomes will be measured in a standardized manner using the Modified Rankin Scale, a commonly utilized six-point scale measuring functional outcome and disability in patients with stroke. The mRS measures independence and dependence related to activities of daily living and can be used over time to determine recovery or regression.

Study monitors will have clinical research experience and be proficient at study monitoring. Study data will be source data verified (SDV) using the subject's medical records, study source worksheets, clinic notes, and radiographic reports as applicable as source documentation.

11. Ethics and Protection of Human Subjects

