Sample Size:	A total of 160 subjects will be enrolled into the study.
Number of Sites:	Up to 28 clinical sites in the US
Study Population:	Subjects with unruptured, angiographically confirmed wide-neck (\geq 4 mm or a dome-to-neck ratio $<$ 2) intracranial aneurysms located at the bifurcation of the basilar artery, carotid terminus, MCA and ACOM arising from the parent vessel for the target aneurysm with a diameter of 2.0 mm to 4.5 mm will be eligible for the study.

Study Procedures:

The study evaluation time points include:

1. Screening/Baseline
2. Procedure
3. Hospital Discharge
4. 30 Day Follow-up (Clinic Visit)
5. 180 Day Follow-up (Clinic Visit)
6. 1 Year Follow-up (Clinic Visit and DSA)
7. 2 Year Follow-up (Telephone Call)
8. 3 Year Follow-up (Clinic Visit and DSA or MRA)
9. 4 Year Follow-up (Telephone Call)
10. 5 Year Follow-up (Clinic Visit and DSA or MRA)

Primary Safety Endpoint:

Composite of Neurological Death or Major Ipsilateral Stroke (in downstream territory) up to 1 year post-procedure:

- *Stroke is defined as rapidly developing clinical signs of focal (or global) disturbance of cerebral function lasting more than 24 hours with no apparent cause other than of vascular origin, including ischemic stroke and/or hemorrhagic stroke (i.e., intraparenchymal hemorrhage (IPH), subarachnoid hemorrhage (SAH), subdural hemorrhage (SDH), epidural hemorrhage (EDH)). [Hatano 1976].*
- *Major Stroke is defined as stroke with symptoms persisting for more than 24 hours AND a sudden increase in the NIHSS of the subject by ≥ 4 .*

Primary Effectiveness Endpoint:

Complete Occlusion:

Rate of complete aneurysm occlusion (Raymond I) without significant parent artery stenosis ($> 50\%$ stenosis) or prior retreatment at 1 year post-procedure.

Secondary Effectiveness Endpoints:

- Technical Success is defined as successful implantation of device— physician able to access target aneurysm, deploy PulseRider® device at the neck of aneurysm and device was detached successfully
- Ability to retain embolic coils within aneurysm immediately post-procedure (as evaluated by the core lab)
- Complete aneurysm occlusion at 3 years and 5 years
- Adequate aneurysm occlusion (defined as Raymond I and II combined) at 1 year, 3 years and 5 years

- The percentage of target aneurysms that are retreated through 1 year, 3 years and 5 years
- The percentage of subjects with significant stenosis defined as $> 50\%$ at implant site at 1 year, 3 years and 5 years.

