1.5.2. Minimization of Risk

Efforts will be made to minimize the potential risks through the following:

1. Investigators who participate in the study will be experienced and skilled in neuro-intervention surgery and will have adequate resources to conduct the clinical study.
2. The study has been designed to ensure treatment and follow-up of subjects are consistent with current medical practice.
3. Each investigator will ensure oversight and approval of the study by the IRB prior to initiation of the study at the investigation site.
4. The investigator and study personnel will be trained on the study protocol.
5. The investigators and appropriate personnel will undergo training on the use of the PulseRider device prior to first use during the study.
6. Subjects will be carefully evaluated against the inclusion/exclusion criteria prior to being enrolled in the study to ensure that their diagnosis and medical status are appropriate for participation.
7. Subject status will be monitored by the investigator or designee throughout the follow-up period as defined in the study protocol.

8. The investigator or designee will evaluate the subject for any adverse events potentially related to the procedure or to the device. Device status will also be assessed using appropriate imaging modalities defined in the study protocol.
9. All reportable adverse events for the study will be reviewed and adjudicated by a CEC.
10. Data from all investigation sites will be monitored throughout the study to evaluate protocol compliance and identify any issues that may affect the safety and welfare of the subjects.
11. De-identified angiograms will be reviewed by an independent core laboratory to assess PulseRider device placement and occlusion of the aneurysm. Sites are requested to provide de-identified images to the core lab. In the event, images are received with any patient identifiers, the core lab's proprietary software removes all patient protected health information (PHI) as images are processed through their system. Each image is then reviewed by a radiology technician to ensure that all PHI was adequately removed. This two-fold process is completed before image exam is uploaded and reviewed. The radiology technician/assessor will also be blinded to the subject's previous medical history.

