3.2. Study Endpoints

3.2.1. Primary Endpoint - Safety

Composite of Neurological Death or Major Ipsilateral Stroke (in downstream territory) up to 1 year post-procedure:

Stroke is defined as rapidly developing clinical signs of focal (or global) disturbance of cerebral function lasting more than 24 hours with no apparent cause other than of vascular origin, including ischemic stroke and/or hemorrhagic stroke (i.e., intraparenchymal hemorrhage (IPH), subarachnoid hemorrhage (SAH), subdural hemorrhage (SDH), epidural hemorrhage (EDH)) [Hatano 1976].

Major Stroke is defined as stroke with symptoms persisting for more than 24 hours AND a sudden increase in the NIHSS of the subject by > 4 .

Minor Stroke is defined as stroke with symptoms persisting for more than 24 hours and a sudden increase in the NIHSS of the subject by 1-3.

TIA is defined as stroke symptoms resolving within ≤ 24 hours.

This endpoint will be adjudicated by the independent Clinical Events Committee (CEC).

[figure not shown]

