- **National Institutes of Health Stroke Scale – NIHSS.** The NIHSS is a standardized clinical assessment tool that provides a quantitative measure of stroke-related neurologic deficit. It is widely used to evaluate stroke severity, determine appropriate treatment, and predict patient outcome. The NIHSS will be performed by qualified personnel. All study personnel performing the NIHSS assessment will be required to have training on the administration of the NIHSS assessment. A valid certification of completion of training will be stored in the site study files.
- **Modified Rankin Scale – mRS.** The mRS is a scale commonly used to measure the degree of disability or dependence in the daily activities in patients following stroke or other neurologic event and is conducted by qualified personnel. It is a scale with six categories ranging from no symptoms to severe disability and death. All study personnel

performing the mRS assessment will be required to have training on the administration of the mRS assessment. Documentation of completion of training will be stored in the site study files and updated at least every 2 years.

- **Baseline aneurysm imaging evaluation.** The baseline imaging evaluation may be a DSA or CTA. The baseline imaging must be reviewed and approved by the Image Screening Committee. As the status of the target aneurysm may change between the baseline image and procedure, a DSA is required prior to enrollment on the procedure day to confirm that the subject remains eligible for the study.
- **Image Screening Committee.** During initial subject screening, the site will submit a de-identified image (either DSA or CTA) to the core lab. Core lab personnel will submit the de-identified baseline image to the Image Screening Committee who will review the image for approval or disapproval. The decision of the committee will be based on their review of the appropriateness as outlined in the Image Screening Committee charter. Upon decision from the Image Screening Committee, the site will be informed of the subject approval/disapproval.

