8.1. Specific Safety Parameters

8.1.1. Adverse Event (AE)

An adverse event (AE) is defined as any untoward medical occurrence, unintended disease or injury, or untoward clinical signs (including abnormal laboratory findings) in subjects, users or other persons, whether or not related to the investigational medical device (ISO 14155:2011E).

- Note 1: This definition includes events related to the investigational medical device or the comparator
- Note 2: This definition includes events related to the procedures involved
- Note 3: For users or other persons, this definition is restricted to events related to the investigational medical devices

For the purposes of this protocol, adverse events will be reported and recorded (via eCRF) if any of the following apply:

- The event is neurological in nature
- The event is a serious adverse event
- Causality is related to:
 - the device
 - the procedure
 - dual antiplatelet medication
 - if causality is unknown

Any medical condition that is present at the time the participant is screened or prior to the start of the study procedure will be considered as baseline and not reported as an AE. Such conditions should be added to medical history, if not previously reported.

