8.5. Clinical Events Committee

The Clinical Events Committee (CEC) will consist of a minimum of three independent physicians with expertise in neurosurgery, neurology or interventional neuroradiology and who are not otherwise involved with the study. The CEC will review all reportable adverse events to adjudicate the safety endpoint, in addition to AEs of interest specified in the CEC charter.

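### A recorded NIHSS rise reaches the CEC only through a site-filed adverse event, and Section 7.10 makes some of that filing discretionary; any event lost favours the device

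*Combined protocol and SAP*

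**What the plan says.** All references are to the combined protocol and SAP.

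- **Endpoint.** The primary safety endpoint is neurological death or major ipsilateral stroke up to 1 year. Major stroke requires symptoms beyond 24 hours "AND a sudden increase in the NIHSS of the subject by" a threshold. As printed, the threshold is 4 or more in the Protocol Summary and more than 4 in Section 3.2.1, where minor stroke is a rise of 1 to 3.
- **Who scores.** Section 7.2.1: "The NIHSS will be performed by qualified personnel". The stated condition is training: "All study personnel performing the NIHSS assessment will be required to have training on the administration of the NIHSS assessment", with a certificate on file. Section 10.4 requires an independent image reader and impartial CEC members. For the clinical scales it relies on standardization: "Clinical outcomes will be measured in a standardized manner using the National Institutes of Health Stroke Scale".
- **When.** The Schedule of Assessments has the NIHSS immediately before the procedure, at discharge, 30 days, 180 days and 1 year, at later clinic visits and at unscheduled visits.
- **What the CEC sees.** Section 8.5: "The CEC will review all reportable adverse events to adjudicate the safety endpoint". Section 10.4 says the same.
- **What must be filed.** Section 8.1.1 lists among its triggers: "The event is neurological in nature". Section 7.10 says that new or unresolved signs or symptoms at an unscheduled visit are reported as an adverse event at the investigator's discretion.
- **Existing safeguards.** On any suspicion of stroke, Section 7.6 requires a stroke-specific AE form, contact with the sponsor, and neurological exam, NIHSS and mRS. Sections 8.3 and 8.4.1 send source documents to adjudication. Section 7.7.2 asks outside physicians for an NIHSS. Sections 9 and 10.4 provide monitoring and source data verification.

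**The concern.** The NIHSS is recorded at every clinic visit, yet no section sends a recorded rise to the CEC. A rise that the site does not file as an adverse event stays in the database unadjudicated. Sections 8.1.1 and 7.10 give different filing rules for new neurological signs at an unscheduled visit, which is a likely place for a stroke to come to light.

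The planned missing-data methods would not recover such an event. Under Section 10.3.4, a subject who completes the 1-year follow-up with no endpoint event is a success. A subject with an unfiled stroke who attends that visit is therefore counted as observed and event-free. Imputation does not apply, and the missing-as-failure and tipping-point analyses in Section 10.3.10 do not touch that subject.

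The error runs one way. There is no control arm to share it, and the test asks whether the upper confidence bound lies below a fixed 15%.

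**Working it through.** **Inputs.** Goal 15%, expected rate 7%, 160 subjects, 10% attrition, stated safety power 80% (Section 10.2). Rule: upper two-sided 95% normal-approximation bound below 15% (Section 10.3.4). Evaluable n = 160 × 0.9 = 144.

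**1. The plan's own figure.** The method is not stated. A z-test with null variance and continuity correction reproduces it:
- null standard error = √(0.15 × 0.85 / 144) = 0.02976
- alternative standard error = √(0.07 × 0.93 / 144) = 0.02126
- z = (0.15 − 0.07 − 1.96 × 0.02976 − 1/288) / 0.02126 = 0.856
- power = Φ(0.856) = 0.804, against the stated 80%

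**2. Where the rule passes.** Upper bound = x/n + 1.96 × √[(x/n)(1 − x/n)/n].

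| Events | Rate | Upper bound | Result |
|---|---|---|---|
| 14/144 | 9.72% | 14.56% | pass |
| 15/144 | 10.42% | 15.41% | fail |
| 16/160 | 10.00% | 14.65% | pass |
| 17/160 | 10.62% | 15.40% | fail |

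One event decides the result at the boundary. It is worth 1/144 = 0.7 points, or 1/160 = 0.6 points. The n = 160 rows treat every subject as observed and ignore between-imputation variance.

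**3. Effect of lost events.** Let u be the share of all composite events that never reach adjudication. The documents give no value, so u is an assumption. The observed event probability is p(1 − u), and the chance of passing is P[X ≤ c] for X ~ Binomial(n, p(1 − u)). At a true p of 15%:

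| u (assumed) | p(1 − u) | n = 144, c = 14 | n = 160, c = 16 |
|---|---|---|---|
| 0 | 15.00% | 4.3% | 4.3% |
| 2% | 14.70% | 5.3% | 5.3% |
| 5% | 14.25% | 7.1% | 7.2% |
| 10% | 13.50% | 11.1% | 11.6% |

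At the planned 7% and n = 144, the chance of passing moves from 92.0% to 94.3% at u = 5% and to 96.1% at u = 10%. The effect matters when the device is near the goal, and little if it performs as expected.

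**4. What u covers.** Neurological death does not depend on the NIHSS. If s is the share of composite events that enter only as a major stroke, and v the share of those lost, then u = s × v. So u cannot exceed v.

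**The case against.** The strongest reply is that filing is mandatory and the CEC has more than a score. Section 8.1.1 covers every neurological event, and Section 8.4.2 gives 72 hours for a serious one. Section 7.6 is triggered by mere suspicion of stroke and calls for MRI or CT if indicated. The CEC receives procedure reports, physician and nursing notes and discharge summaries. Monitors compare the database with the medical record, so an NIHSS rise with no adverse event is a gap they should find. The CEC charter and the monitoring plan are not among the documents and may already hold a trigger.

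Most of this stands, and it rules out several stronger readings that a reader might infer:

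- *That the CEC can only accept the site's score.* Sections 8.3 and 8.4.1 give it source documents with which to question a low one.
- *That the implanting physician decides the endpoint.* Nothing bars that physician from scoring, but nothing assigns the task to that physician either, and the CEC adjudicates.
- *That under-calling will occur.* The text permits it but gives no evidence of it or of its frequency.
- *That a higher chance of passing at a true rate such as 12% is a false pass.* That rate is below 15%, so the alternative in Section 10.1.1 is true and passing is correct.

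Two things remain. The safeguards act on events that are filed or that a monitor notices; none of the sections refers an unfiled rise to the CEC. And Section 7.10 contradicts Section 8.1.1 on whether such an event must be filed.

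**Conclusion.** The point holds as a gap in event capture. The protocol collects the score that helps define major stroke, but it describes no path from that score to the CEC except a site-filed adverse event, and it gives inconsistent rules on filing. Existing safeguards lower the risk without removing it, and any loss favours the device.

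The size depends on u: for 2% to 10% of all composite events lost, the chance of wrongly passing at a true 15% goes from 4.3% to between 5.3% and 11.1% at n = 144, with similar results at n = 160. These figures illustrate sensitivity and are not an estimate for this trial. The conclusion also assumes that the unseen CEC charter has no such trigger. This is an inexpensive improvement; it does not show that the safety analysis is invalid.

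**What to change.** 1. **Reconcile the threshold** between the Protocol Summary (4 or more) and Section 3.2.1 (more than 4). As printed, Section 3.2.1 leaves a rise of exactly 4 neither major nor minor.
2. **Sections 8.5 and 10.4:** the EDC automatically refers to the CEC any subject whose recorded post-procedure NIHSS, at a scheduled or unscheduled visit, exceeds the pre-procedure score by the reconciled major-stroke threshold, whether or not an adverse event was filed. If the charter already provides this, state it in the protocol.
3. **Reconcile Section 7.10 with Section 8.1.1** so that reporting of new neurological signs at an unscheduled visit is not discretionary.
4. **Section 7.2.1, secondary:** where existing trained site staff allow, post-procedure NIHSS and mRS are scored by someone other than the physician who implanted that subject's device.

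The cost is protocol wording, one check on data already collected, a few extra CEC reviews and some scheduling effort for item 4. No visits or subjects are added.

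The referral catches recorded rises that were not filed. It cannot catch a score set too low, or a deficit that resolved before the visit. Item 4 reduces the first of these only in part, since the rater would still be unblinded and at the same site.

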11.1. Ethical Standard

As the Sponsor of this study, Pulsar Vascular, Inc. has the overall responsibility for the conduct of the study, including assurance that the study is in accordance with the ethical principles that have their origin in the Declaration of Helsinki, as well as the regulatory requirements of the Food and Drug Administration and local government. The Sponsor will also maintain compliance with Good Clinical Practice (International Conference on Harmonization (ICH) version 4 du 1 May 1996), the European standard EN ISO 14155:2011 (Clinical Investigation of Medical Devices for Human Subjects), Sponsor general responsibilities (21 CFR 812.40), selection of investigators (21 CFR 812.43), monitoring (21 CFR 812.46), supplemental applications (21 CFR 812.35 [a] and [b]), maintaining records (21 CFR 812.140 [b]), and submitting reports (21 CFR 812.150 [b])), and to local regulations where required.

- General Responsibilities

Sponsor's general duties consist of submitting the IDE application to FDA, assuring that sites have received IRB approvals prior to shipping the devices, selecting investigators, ensuring proper clinical site monitoring and ensuring subject informed consent is obtained. Any additional requirements imposed by an IRB or regulatory authority shall be followed, if appropriate.

- Data Quality and Reporting

Sponsor is responsible for providing quality data that satisfy federal regulations and informing proper authorities of unanticipated adverse effects and deviations from the protocol.

- Selection of Investigators

Sponsor will select qualified investigators, obtain a signed Investigator Agreement and provide the investigators with the information necessary to conduct the study.

- Supplemental Applications—Protocol Amendments

As appropriate, Sponsor will submit changes in the study protocol to the FDA and investigators to obtain IRB re-approval. A justification for each amendment will be documented.

- Maintaining Records

Sponsor will maintain copies of correspondence, device shipment and disposition records, data, adverse device effects and other records related to the study. Sponsor will maintain records related to the signed Investigator Agreements and financial disclosure.

- Submitting Reports

Sponsor will submit any required regulatory reports identified in this section of the regulation. This includes unanticipated adverse device effects, withdrawal of FDA approval, current investigators list, annual progress reports, recall information, final reports and device use without informed consent.

